9.4.5. Columbia Suicide Severity Rating Scale

The C-SSRS captures the occurrence, severity, and frequency of suicidal ideation and/or behavior during the assessment period. The scale includes suggested questions to solicit the type of information needed to determine if suicidal ideation and/or behavior occurred. The C-SSRS is administered by appropriately trained site personnel. The tool was developed by the National Institute of Mental Health trial group for the purpose of being a counterpart to the Columbia Classification Algorithm of Suicide Assessment categorization of suicidal events. For this study, the scale has been adapted (with permission from the scale authors) to include only the portion of the scale that captures the occurrence of the 11 preferred ideation and behavior categories.

The nonleading AE collection should occur prior to the collection of the C-SSRS. If a suicide-related event is discovered *during the C-SSRS* but was not captured during the nonleading AE collection, sites should not change the AE form. If an event is serious or leads to discontinuation, this is an exception where the SAE and/or AE leading to discontinuation should be included on the AE form and the process for reporting SAEs should be followed.

9.4.6. Self-Harm Supplement and Follow-Up Forms

Suicide-related events (behavior and/or ideations) will be assessed and evaluated with each administration of the C-SSRS. The Self-Harm Supplement Form is a single question to enter the number of suicidal behavior events, possible suicide behaviors, or nonsuicidal self-injurious behaviors. If the number of behavioral events is greater than zero, it will lead to the completion of the self-harm follow-up form. The Self-Harm Follow-up form is a series of questions that provides a more detailed description of the behavior cases.

9.4.7. Chest X-ray and Tuberculosis Testing

Posteroanterior and lateral chest radiography will be performed at screening for all subjects unless these have been obtained within 90 days prior to initial screening and the radiographs or report is available for investigator review. Variations on the chest radiography view requirements will only be permitted if the country/local guidelines of care for standard TB screening differ from these protocol specifications.

All subjects will undergo a TB test at screening (TST or interferon γ release test). Refer to Exclusion Criterion [17] for details regarding TB testing.

See Section [6.4](#) for subjects who are rescreening for this study and have undergone radiography and/or TB testing as part of their initial screening.

9.4.8. Hepatitis B Virus DNA Monitoring

Subjects whose results are HBsAg negative and HBcAb positive (and/or HBsAb positive in Japan) at screening, will have an HBV DNA test performed by the central laboratory. Subjects whose results are HBV DNA negative (undetectable) may be enrolled into the study, according to investigator judgment, with HBV DNA monitoring as detailed in the Schedule of Activities (Section 2). If the result of the HBV DNA testing becomes positive at any time during the study, the subject will be permanently discontinued from IP (see Section 8.1) and should receive appropriate follow-up medical care, including consideration for antiviral therapy. A specialist physician in the care of subjects with hepatitis (for example, infectious disease physician or hepatologist) should be consulted. The timing of discontinuation from the study drug and any other immunosuppressant therapy should be based on the recommendations of the consulting specialist physician in conjunction with the investigator and medical guidelines/standard of care.

9.4.9. Immunogenicity Assessments

At the visits and times specified in the Schedule of Activities (Section 2), venous blood samples will be collected to determine antibody production against the LY3375880. To interpret the results of immunogenicity, a PK sample will be collected at the same time points as the immunogenicity sample. All samples for immunogenicity should be taken predose. Instructions for the collection and handling of blood samples will be provided by the sponsor. The actual date and time (24-hour clock time) of each sampling will be recorded.

In addition, subjects who were deemed responders at Week 16 may be prompted to collect an immunogenicity sample at the first scheduled visit where loss of response is observed (i.e., EASI-25 was not achieved) in the maintenance period. This will allow an evaluation of ADA status at the time of retreatment for subjects randomized to placebo until loss of response during the maintenance period. To prevent unblinding of treatment regimen, all subjects who are deemed responders at Week 16 will have PK and immunogenicity collected upon loss of response.

Immunogenicity will be assessed by a validated assay designed to detect ADA in the presence of the LY3375880 at a laboratory approved by the sponsor. Antibodies may be further characterized and/or evaluated for their ability to neutralize the activity of LY3375880.

Treatment-emergent ADA positive (TE ADA+) are defined in Section 10.2.6.

Samples will be retained for a maximum of 15 years after the last subject visit, or for a shorter period if local regulations and ethical review boards (ERBs) allow, at a facility selected by the sponsor. The duration allows the sponsor to respond to future regulatory requests related to the LY3375880. Any samples remaining after 15 years will be destroyed.

9.4.10. Safety Monitoring

Lilly will periodically review evolving aggregate safety data within the study by appropriate methods. In the event that safety monitoring uncovers an issue that needs to be addressed by

unblinding at the group level, members of an internal assessment committee can view unblinded data and conduct additional analyses of the unblinded safety data. The internal assessment committee is composed of personnel who do not have direct site contact or data entry/validation responsibilities. Details are specified in the statistical analysis plan (SAP). In addition, the Safety Internal Review Committee and the Global Subject Safety expedited reporting team can also unblind at the individual SAE case level, when appropriate.

9.4.10.1. Hepatic Safety Monitoring

If a study subject experiences elevated ALT ≥ 3 x ULN, ALP ≥ 2 x ULN, or elevated TBL ≥ 2 x ULN, liver testing should be repeated within 3 to 5 days including ALT, AST, ALP, TBL, direct bilirubin, gamma-glutamyl transferase, and creatine kinase to confirm the abnormality and to determine if it is increasing or decreasing. If the abnormality persists or worsens, clinical and laboratory monitoring should be initiated by the investigator and in consultation with the study medical monitor. Monitoring of ALT, AST, TBL, and ALP should continue until levels normalize or return to approximate baseline levels.

Discontinuation criteria of IPs, either temporary interruption or permanent discontinuation, due to abnormal ALT, AST, TBL, or ALP, are detailed in Section 8.

Hepatic Safety Data Collection

Additional safety data should be collected via the hepatic eCRF if 1 or more of the following conditions occur:

- elevation of serum ALT to ≥ 5 x ULN on 2 or more consecutive blood tests
- elevated serum TBL to ≥ 2 x ULN (except for cases of known Gilbert's syndrome)
- elevation of serum ALP to ≥ 2 x ULN on 2 or more consecutive blood tests
- subject discontinued from treatment due to a hepatic event or abnormality of liver tests
- hepatic event considered to be an SAE.

See Appendix 4 for a description of selected tests that may be obtained in the event of a treatment-emergent hepatic abnormality.

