8.1. Discontinuation from Study Treatment

8.1.1. Permanent Discontinuation from Study Treatment

Possible reasons leading to permanent discontinuation of IP:

- **Subject Decision**
 - the subject requests to discontinue IP.
- **Discontinuation due to a hepatic event or liver test abnormality:** Subjects who are discontinued from IP due to a hepatic event or liver test abnormality should have additional hepatic safety data collected via designated data transmission methods. Discontinuation of the IP for abnormal liver tests **should be** considered by the investigator when a subject meets one of the following conditions after consultation with the Lilly-designated medical monitor:
 - ALT or AST >8x upper ULN
 - ALT or AST >5x ULN for more than 2 weeks.
 - ALT or AST >3x ULN and TBL level >2x ULN or international normalized ratio (INR) >1.5.
 - ALT or AST >3x ULN with the appearance of fatigue, nausea, vomiting, right upper-quadrant pain or tenderness, fever, rash, and/or eosinophilia (>5%).
 - ALP >3x ULN
 - ALP >2.5x ULN and TBL >2x ULN
 - ALP >2.5x ULN with the appearance of fatigue, nausea, vomiting, right quadrant pain or tenderness, fever, rash, and/or eosinophilia (>5%).
- **Discontinuation due to HBV DNA results**
 - Subjects who are HBcAb positive (and/or HBsAb positive in Japan) at screening and are enrolled in the study will be discontinued from the IP if the result of the HBV DNA testing becomes detectable at any time during the study.

Subjects who discontinue the IP early will continue in the study according to the Schedule of Activities (Section 2), unless there is a reason to discontinue from the study (Section 8.2).

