Appendix 2. Clinical Laboratory Tests

Hematology^{a,b}

Hemoglobin
Hematocrit
Erythrocyte count (RBC)
Mean cell volume
Mean cell hemoglobin
Mean cell hemoglobin concentration
Leukocytes (WBC)
Platelets

Absolute counts of:

Neutrophils, segmented
Neutrophils, juvenile (bands)
Lymphocytes
Monocytes
Eosinophils
Basophils

Urinalysis^{a,b,c}

Specific gravity
pH
Protein
Glucose
Ketones
Bilirubin
Urobilinogen
Blood
Nitrite

Clinical Chemistry^{a,b}

Serum Concentrations of:
Sodium
Potassium
Bicarbonate
Chloride
Total bilirubin
Direct bilirubin
Alkaline phosphatase
Alanine aminotransferase (ALT)
Aspartate aminotransferase (AST)
Gamma-glutamyl transferase (GGT)
Blood urea nitrogen (BUN)
Creatinine with calculated eGFR
Calcium
Phosphorus
Glucose (random, fasting)
Albumin
Total protein
Fasting lipid profile^d

Other Tests^a

Hepatitis B surface antigen (HBsAg)^e
Anti-Hepatitis B core antibody (HBcAb)^e
HBV DNA^f
Anti-Hepatitis B surface antibody (HBsAb)^e
Human immunodeficiency virus (HIV)^e
Hepatitis C antibody^{e,g}
Exploratory (Long Term) storage samples (serum, plasma)
DNA for epigenetics, and mRNA
Pharmacogenetic sample
Pregnancy Test^h
Follicle-stimulating hormone^{e,i}
Serum immunoglobulin (total and allergen-specific IgE)
QuantiFERON[®]-TB Gold or T-SPOT[®].TB^j
PPD (local testing)
LY3375880 plasma levels
Target engagement (Total IL-33)
Immunogenicity
IL-19
TARC
Periostin

Abbreviations: eGFR = estimated glomerular filtration rate; HBV = hepatitis B virus; IgE = immunoglobulin E; IL = interleukin; PPD = purified protein derivative; RBC = red blood cell; TARC = thymus and activation-regulated chemokine; TB = tuberculosis; WBC = white blood cell.

- a Assayed by sponsor-designated laboratory.
- b Unscheduled or repeat blood chemistry, hematology, and urinalysis panels may be performed at the discretion of the investigator, as needed.
- c Microscopic examination of sediment performed only if abnormalities are noted on the routine urinalysis.
- d Fasting lipid profile. Subjects should not eat or drink anything except water for 12 hours prior to test. If a subject attends these visits in a nonfasting state, this will not be considered a protocol violation.
- e Test required at Visit 1 only to determine eligibility of subject for the study.
- f For subjects who meet criteria for HBV DNA testing at screening and HBV DNA monitoring in the study (Section 9.4.8).
- g A positive hepatitis C antibody result will be confirmed with an alternate hepatitis C method.

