Appendix 4. Hepatic Monitoring Tests for Treatment-Emergent Abnormality

Selected tests may be obtained in the event of a treatment-emergent hepatic abnormality and may be required in follow-up with subjects in consultation with the Lilly, its designee, or the clinical research physician.

Hepatic Monitoring Tests

Hepatic Hematology^a

Hemoglobin
Hematocrit
RBC
WBC
Neutrophils, segmented
Lymphocytes
Monocytes
Eosinophils
Basophils
Platelets

Hepatic Chemistry^a

Total bilirubin
Direct bilirubin
Alkaline phosphatase
ALT
AST
GGT
CPK

Haptoglobin^a

Hepatic Coagulation^a
Prothrombin time
Prothrombin time, INR

Hepatic Serologies^{a,b}

Hepatitis A antibody, total
Hepatitis A antibody, IgM
Hepatitis B surface antigen
Hepatitis B surface antibody
Hepatitis B core antibody
Hepatitis C antibody
Hepatitis E antibody, IgG
Hepatitis E antibody, IgM

Anti-nuclear antibody^a

Alkaline phosphatase isoenzymes^a

Anti-smooth muscle antibody (or anti-actin antibody)^a

Abbreviations: ALT = alanine aminotransferase; AST = aspartate aminotransferase; CPK = creatinine phosphokinase; GGT = gamma-glutamyl transferase; Ig = immunoglobulin; INR = international normalized ratio; RBC = red blood cell; WBC = white blood cell.

^a Assayed by Lilly-designated or local laboratory.

^b Reflex/confirmation dependent on regulatory requirements and/or testing availability.

Appendix 5. Examples of Infections That May Be Considered Opportunistic in the Setting of Biologic Therapy

Bacterial
Bartonellosis (disseminated disease only)
Campylobacteriosis (invasive disease only)
Legionellosis
Listeria monocytogenes (invasive disease only)
Nocardiosis
Tuberculosis
Non-tuberculous mycobacterial disease
Salmonellosis (invasive disease only)
Shigellosis (invasive disease only)
Vibriosis (invasive disease due to Vibrio vulnificus)
Viral
BK virus disease including polyomavirus-associated nephropathy
Cytomegalovirus disease
Hepatitis B virus reactivation
Hepatitis C virus progression
Herpes simplex (invasive disease only)
Herpes zoster (any form)
Post-transplant lymphoproliferative disorder (Epstein-Barr virus)
Progressive multifocal leukoencephalopathy (PML), John Cunningham (JC) virus [excluded from the study]
Fungal
Aspergillosis (invasive disease only)
Blastomycosis
Candidiasis (invasive disease or pharyngeal)
Coccidioidomycosis
Cryptococcosis
Histoplasmosis
Paracoccidioides infections
Penicillium marneffei
Pneumocystis jirovecii (formerly Pneumocystis carinii)

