#### **5.13.6.1. Abnormal Hepatic Tests**

Analyses for abnormal hepatic tests will involve 4 laboratory analytes: ALT, AST, total bilirubin, and ALP. In addition to the analyses described in Section 5.13.3, this section describes specific analyses for this topic.

The central laboratory reference ranges (CLRM reference ranges) will be used for these laboratory assessments (ALT, AST, total bilirubin, and ALP).

Analyses for change from baseline to last observation, change from the baseline value to the minimum value during the Induction/Maintenance Period, change from the baseline value to the maximum value during the Induction/Maintenance Period, and treatment-emergent high or low laboratory results at any time are described in Section 6.13.3.

The patients with the following abnormal elevations in hepatic laboratory tests at any time will be listed for both the Induction and Maintenance periods:

- ALT measurement  $\geq 3$  times,  $\geq 5$  times and  $\geq 10$  times the central laboratory ULN.
- AST measurement  $\geq 3$  times,  $\geq 5$  times and  $\geq 10$  times the central laboratory ULN.
- Total bilirubin measurement  $\geq 2$  times the central laboratory ULN.
- ALP measurement  $\geq 1.5$  times the central laboratory ULN.

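### Protocol Section 9.4.10.1 leaves AST out of the 3 to 5 day repeat-test trigger and the hepatic eCRF laboratory triggers, although Section 8.1.1 treats AST like ALT

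*Protocol*

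**What the plan says.** **Repeat test (Protocol 9.4.10.1).** The trigger is ALT at least 3x ULN, ALP at least 2x ULN, or TBL at least 2x ULN. Then "liver testing should be repeated within 3 to 5 days including ALT, AST, ALP, TBL, direct bilirubin, gamma-glutamyl transferase, and creatine kinase". After that, "If the abnormality persists or worsens, clinical and laboratory monitoring should be initiated by the investigator and in consultation with the study medical monitor", and ALT, AST, TBL and ALP are followed until they are normal or near baseline.

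**Hepatic eCRF (same section).** "Additional safety data should be collected via the hepatic eCRF if 1 or more of the following conditions occur". The laboratory conditions are ALT at least 5x ULN on two consecutive tests, TBL at least 2x ULN (known Gilbert's syndrome excepted), and ALP at least 2x ULN on two consecutive tests. The other two conditions are discontinuation of treatment for a hepatic reason and a hepatic SAE.

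**Discontinuation (Protocol 8.1.1).** Stopping IP because of liver results is a step to be "considered by the investigator when a subject meets one of the following conditions after consultation with the Lilly-designated medical monitor". All four aminotransferase conditions apply to either enzyme at the same multiple. One of them is "ALT or AST >5x ULN for more than 2 weeks".

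**Discretionary testing.** Appendix 2, footnote b: "Unscheduled or repeat blood chemistry, hematology, and urinalysis panels may be performed at the discretion of the investigator, as needed". Appendix 4: "Selected tests may be obtained in the event of a treatment-emergent hepatic abnormality and may be required in follow-up".

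**Analysis (SAP 5.13.6.1).** "Analyses for abnormal hepatic tests will involve 4 laboratory analytes: ALT, AST, total bilirubin, and ALP". Patients are listed at 3, 5 and 10 times ULN for ALT and for AST alike.

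**The concern.** The protocol accepts AST alone as a reason to consider stopping IP, but does not let AST alone start the confirmatory test. It gives no reason for the difference. Two subjects with the same size of aminotransferase rise are handled differently: one gets a confirmatory panel within days, and the other may wait for the next scheduled visit.

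Two things are at stake. The first is prompt confirmation of a possible liver signal, including the creatine kinase and GGT results that help to show its origin. The second is the extra detail on the hepatic eCRF, which would not be collected for a repeated AST rise that stays isolated and does not lead to discontinuation. The primary endpoint, power and type I error are not involved.

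**Working it through.** **Step 1. Set the rules side by side.**

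| Rule | ALT | AST | ALP | TBL |
|---|---|---|---|---|
| Screening exclusion [16] | ≥2x | ≥2x | ≥2x | ≥1.5x |
| 3 to 5 day repeat trigger (9.4.10.1) | ≥3x | none | ≥2x | ≥2x |
| Hepatic eCRF laboratory trigger (9.4.10.1) | ≥5x, twice | none | ≥2x, twice | ≥2x |
| Consider discontinuation (8.1.1) | >8x; >5x for over 2 weeks; >3x with TBL >2x or INR >1.5; >3x with symptoms or eosinophilia | same as ALT | >3x; >2.5x with TBL >2x or symptoms or eosinophilia | >2x, in combination only |
| SAP listing (5.13.6.1) | ≥3x, ≥5x, ≥10x | same as ALT | ≥1.5x | ≥2x |

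AST is the only one of the three enzymes with a discontinuation threshold but no repeat trigger. Elsewhere ALT and AST share the same multiples.

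**Step 2. Define the affected case.** An isolated AST rise has AST ≥3x ULN with ALT <3x, ALP <2x and TBL <2x ULN. None of the three triggers is met, so any recheck before the next scheduled chemistry is discretionary.

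**Step 3. Time to the next required AST.** Inputs from the Schedule of Activities (Table FCAB.1):
- Chemistry at Days 0, 14, 28, 56, 84 and 112, then every 28 days to 364, and at 420.
- Windows of ±2 days at Visits 4 and 5, ±4 days at Visits 6 to 17, and ±5 days at Visit 801.

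Formula: nominal gap = later day − earlier day; range = nominal gap ± (sum of the two windows).

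| First seen at | Next chemistry | Nominal gap (days) | Range (days) |
|---|---|---|---|
| Visit 4 | Visit 5 | 28 − 14 = 14 | 14 ± (2 + 2) = 10 to 18 |
| Visit 5 | Visit 6 | 56 − 28 = 28 | 28 ± (2 + 4) = 22 to 34 |
| Visits 6 to 16 (11 intervals) | Visits 7 to 17 | 28 | 28 ± (4 + 4) = 20 to 36 |
| Visit 17 | Visit 801 | 420 − 364 = 56 | 56 ± (4 + 5) = 47 to 65 |

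For Visits 5 to 16 the gap is nominally 28 days, overall range 20 to 36. The same ALT rise is rechecked at 3 to 5 days. The AST recheck is therefore nominally 28 − 5 = 23 to 28 − 3 = 25 days later than the ALT recheck, and 20 − 5 = 15 to 36 − 3 = 33 days later across the windows.

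**Step 4. Effect on dosing.** IP is given at Visit 2 and at Visits 5 to 17. For a rise first seen at Visits 5 to 16, the next required AST is drawn at the next dosing visit. For ALT, the repeat result precedes that dose by at least 20 − 5 = 15 days, less laboratory turnaround, which is not stated. So one dose decision may rest on a single AST value unless the investigator orders a retest. After Visit 17 no IP is scheduled, so the longer gap there affects no dose.

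**Step 5. What the other criteria already cover.** AST >8x ULN, and AST >3x ULN with raised TBL or INR, symptoms or eosinophilia, can prompt discontinuation without any persistence requirement. What remains is mainly an isolated, asymptomatic AST of about 5 to 8x ULN, where the criterion depends on duration, and a lower AST rise that would simply have been confirmed sooner had it been ALT.

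**The case against.** The case on the other side has four parts.

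- **Different purposes.** Retest triggers and discontinuation criteria need not match. ALP also differs: ≥2x to retest, but >2.5x or >3x to consider stopping. This is fair. But the ALP trigger sits below its stopping level, as an early check should, whereas AST has no trigger at any level.
- **Specificity.** AST is less specific to the liver than ALT, so some repeats would be for muscle-related rises. That stands as a cost. It does not explain why AST alone is good enough for considering discontinuation.
- **Safeguards.** AST is in every chemistry panel. Section 9.2 requires documented investigator review of each laboratory report. Unscheduled tests are allowed, the sponsor reviews aggregate safety data, and discontinuation is only to be considered. These points stand and lower the severity. None of them sets a retest date.
- **No AST value is lost.** This is correct. AST is analysed under SAP 5.13.6.1, and an AST rise that leads to discontinuation, or a hepatic SAE, still reaches the hepatic eCRF. Only the supplementary detail for the other isolated AST rises is missing.

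A reader might go further and infer that the two-week criterion in Section 8.1.1 cannot work for either enzyme, because no test is required just after day 14. The documents do not support that. Once an abnormality is confirmed by the repeat panel, Section 9.4.10.1 calls for monitoring in consultation with the medical monitor until levels settle. Section 9.2 leaves the frequency of adverse event follow-up to the investigator. A duration of more than two weeks can be shown by any later value. An unstated interval is not a rule that fails.

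**Conclusion.** The point holds for the AST omission only. AST is absent from both trigger lists in Section 9.4.10.1, and this is inconsistent with Section 8.1.1, the screening exclusion and the SAP.

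The size is a required recheck at nominally 28 days (20 to 36) instead of 3 to 5 days, for an isolated AST rise first seen at Visits 5 to 16. Roughly one dose decision is affected, and some hepatic eCRF detail is missed.

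Severity is low. The documents give no frequency for such rises. They are probably rare, since AST of 2x ULN or more at screening is excluded and Section 5.5 reports no clinically significant laboratory changes in subjects given LY3375880 in Phase 1.

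The day counts assume that the rise is first seen at a scheduled visit, that time runs from the date of that sample, and that visits may fall anywhere in their windows.

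**What to change.** Make two wording changes in Protocol Section 9.4.10.1:

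1. In the repeat-test trigger, replace ALT at 3x ULN or more with ALT or AST at 3x ULN or more.
2. In the hepatic eCRF conditions, replace ALT with ALT or AST in the condition that needs 5x ULN or more on two consecutive tests.

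The first change also brings a confirmed AST rise under the follow-up monitoring that the section already describes. The SAP hepatic listings need no change, because they already treat AST like ALT.

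The cost is the amendment wording, a few extra repeat panels and a few more hepatic eCRF entries. Some repeats will be for AST of muscle origin; the creatine kinase already in the panel helps to identify these.

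I would not add a mandatory retest at days 15 to 17. For a rise first seen at Visit 4, the Visit 5 dose can fall 10 to 18 days later, so such a retest could come on or after the dosing day.
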